9. BIOMARKER, CORRELATIVE, AND SPECIAL STUDIES

9.1 Laboratory Correlative Studies

The plasma concentrations of eribulin as well as irinotecan, SN-38 and SN-38 glucuronide will be measured to assess drug disposition and pharmacokinetic parameters in each patient.

- 9.1.1 Pharmacokinetics
- 9.1.1.1 Collection of Specimen(s). Blood plasma samples for pharmacokinetics will be collected during cycle 1 on day 1 at pre-dose and at 15 minutes, 1 hour, 1.5 hours, 2 hours, 4 hours, and 5 hours after the start of the eribulin infusion and a pre-dose sample on day 8. These samples will be required for all patients. An optional sample between 24-96 hours may also be collected after the start of the eribulin infusion, from patients that are available for blood draw. Whole blood samples will be collected from the central line or a peripheral IV provided a flush of at least 10 ml of normal saline has been administered. At each time point, 7 ml of venous blood will be withdrawn into sodium heparinized collection tube. Please refer to Pharmacokinetic Study Form in Appendix G
- 9.1.1.2 Handling of Specimens(s). After collection, blood and anti-coagulant will be mixed by inverting the tube 8–10 times. Blood samples will be placed on ice immediately and centrifuged within 5 min at 7200 g at 4°C for 2 min. Plasma will be transferred into amber plastic tubes and stored on dry ice prior to transferring at -80°C until analysis. Plasma concentrations of free-base eribulin will be quantified using a validated liquid chromatography tandem mass spectrometry (LC/MS/MS) method as previously described [62]. Irinotecan, SN-38 and SN-38 glucuronide concentrations will be quantified using a validated HPLC method with fluorescence detection as previously described [63, 64].
- 9.1.1.3 Shipping of Specimen(s). Samples will be collected by study personnel in [name] lab for storage, processing and analysis. Please see Appendix G for additional information.

9.1.1.4 Site(s) Performing Correlative Study. University of Kentucky and Children's Hospital Colorado

10. STUDY CALENDAR

Evaluations/Material and Data to be Collected

Required Clinical, Laboratory and Disease Evaluation

All clinical and laboratory studies to determine eligibility must be performed within 7 days prior to enrollment unless otherwise indicated. Laboratory values used to assess eligibility (see Section

3.0) must be no older than seven (7) days at the start of chemotherapy. The start of chemotherapy is defined as the initiation of treatment with irinotecan and eribulin. The start of protocol therapy is defined as the initiation of cefixime. Laboratory tests need not be repeated if chemotherapy starts within seven (7) days of obtaining labs to assess eligibility. If a post-enrollment lab value is outside the limits of eligibility, or laboratory values are >7 days old, then the following laboratory evaluations must be re-checked within 48 hours prior to initiating chemotherapy: CBC with differential, bilirubin, ALT (SGPT) and serum creatinine. If the recheck is outside the limits of eligibility, the patient must be re-screened to receive protocol-prescribed chemotherapy.

Imaging studies must be obtained within 14 days prior to start of chemotherapy (repeat the tumor imaging if necessary). For patients whose disease is evaluated with bone marrow studies, the bone marrow aspirates and biopsies are required within 14 days prior to start of chemotherapy.

Studies to be obtained	Pre- Study	During Cycle 1	Prior to Subsequent	Off Treatment	Off study [#]
			Cycles^		
History	Х	Х	Х	Х	Х
Physical Exam with vital signs	Х	Weekly	Х	Х	Х
Height, Weight, BSA	Х	Х	Х		Х
Performance Status	Х		Х		Х
CBC, differential, platelets	Х	Twice	Weekly	Х	Х
		weekly			
Complete metabolic profile	Х	Weekly	Х	Х	Х
Pregnancy test (only females of	Х		Х		
childbearing potential)					
12-lead EKG	Х	X**	X**		
Disease Evaluation	Х	End of	End of cycle 4	Х	
		cycle 2 ^{\$}	then every 3		
			cycles		
Patient Diary*		Х	Х		
Pharmacokinetics (as per Section		X			
9.1 and Appendix G)					

*Patients will be given the diary from Appendix F to fill out with each cycle of treatment. They will return this prior to starting the next cycle

[#]Every effort will be made to follow patients for at least 30 days after the last dose of medication, in order to monitor patients for resolution or late development of adverse events

[^] Labs should be done within 48 hours of initiation of the subsequent cycle of chemotherapy

^{\$} Disease evaluation should be done between days 15-21 of cycle 2

**EKG will be performed prior to Day 8 eribulin during cycle 1, and prior to day 1 eribulin of cycle 2

11. MEASUREMENT OF EFFECT

Although not the primary endpoint of this trial, tumor response will be assessed by standard criteria. For the purposes of this study, patients should be re-evaluated after cycles 2 and 4, and then every third cycle as long as clinically stable.

11.1 Antitumor Effect – Solid Tumors

Response and progression will be evaluated in this study using the new international criteria proposed by the revised Response Evaluation Criteria in Solid Tumors (RECIST) guideline (version 1.1) [65]. Changes in the largest diameter (uni-dimensional measurement) of the tumor lesions and the shortest diameter in the case of malignant lymph nodes are used in the RECIST criteria.

11.1.1 Definitions

Evaluable for toxicity. All patients will be evaluable for toxicity from the time of their first treatment with study medications.

Evaluable for objective response. Only those patients who have measurable or evaluable disease present at baseline, have received at least one cycle of therapy, and have had their disease re-evaluated will be considered evaluable for response. These patients will have their response classified according to the definitions stated below. (Note: Patients who exhibit objective disease progression prior to the end of cycle 1 will also be considered evaluable).

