5.6 Dose Escalating Criteria

A 3 + 3 design will be used to determine dose assignment for patients, as described in Section 13.2. Specifically, the following rules will apply for dose escalation:

- A. Evaluate 3 patients at $dose_k$:
 - 1. If 0 of 3 patients have DLT, then
 - i. If first cohort, increase dose to $dose_{k+1}$ and go to A.
 - ii. Otherwise, go to B.
 - 2. If 1 of 3 patients has DLT, then go to B.
 - 3. If more than 1 patient has DLT
 - i. If lowest dose, then go to C.
 - ii. Otherwise, decrease dose to $dose_{k-1}$ and go to A.
- B. Evaluate 3 additional patients at dose_k :
 - 1. If 0 or 1 of 6 patients has DLT, then increase dose to $dose_{k+1}$ and go to A.
 - 2. If 2 or more patients have DLT, then
 - i. If lowest dose, then go to C.
 - ii. Otherwise, decrease dose to $dose_{k-1}$ and go to A.
- C. Discontinue dose escalation/de-escalation.

Accrual will continue until the recommended phase II dose for a Phase II study (RP2D) is established and at least 6 patients have been treated at this dose. The RP2D is the highest dose level at which no more than 1 of 6 patients experiences first-cycle DLT. Doses higher than dose level 2 will not be studied in this trial. Once the RP2D is identified, an additional 10 patients will be enrolled at this dose level.

5.7 **Duration of Therapy**

In the absence of treatment delays due to adverse event(s), treatment may continue for up to 17 cycles until one of the following criteria applies:

• Disease progression

- Intercurrent illness that prevents further administration of treatment
- Unacceptable adverse event(s)
- Patient decides to withdraw from the study
- General or specific changes in the patient's condition render the patient unacceptable for further treatment in the judgment of the investigator.

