11.1.4.3 Evaluation of Best Overall Response

The best overall response is the best response recorded from the start of the treatment until disease progression/recurrence (taking as reference for progressive disease the smallest measurements recorded since the treatment started). The patient's best response assignment will depend on the achievement of both measurement and confirmation criteria.

Target	Non-Target	New	Overall	Best Overall Response when
Lesions	Lesions	Lesions	Response	Confirmation is Required*
CR	CR	No	CR	≥4 wks. Confirmation**
CR	Non-CR/Non-	No	PR	
	PD			
CR	Not evaluated	No	PR	>1 who Confirmation**
PR	Non-CR/Non-	No	PR	≥ 4 wks. Commutation
	PD/not			
	evaluated			
SD	Non-CR/Non-	No	SD	Desumanted at least once >4
	PD/not			vike from baseline**
	evaluated			wks. nom basenne
PD	Any	Yes or No	PD	
Any	PD***	Yes or No	PD	no prior SD, PR or CR
Any	Any	Yes	PD	
* See RECIST 1.1 manuscript for further details on what is evidence of a new lesion.				
** Only fo	** Only for non-randomized trials with response as primary endpoint.			
*** In exceptional circumstances, unequivocal progression in non-target lesions may be				
accepte	accepted as disease progression.			

For Patients with Measurable Disease (*i.e.*, Target Disease)

Note: Patients with a global deterioration of health status requiring discontinuation of treatment without objective evidence of disease progression at that time should be reported as "*symptomatic deterioration*." Every effort should be made to document the objective progression even after discontinuation of treatment.

For Patients with Evaluable (non-measurable) Disease (*i.e.*, Non-Target Disease)

Non-Target Lesions	New Lesions	Overall Response	
CR	No	CR	
Non-CR/non-PD	No	Non-CR/non-PD*	
Not all evaluated	No	not evaluated	
Unequivocal PD	Yes or No	PD	
Any	Yes	PD	
* 'Non-CR/non-PD' is preferred over 'stable disease' for non-target disease since SD is			
increasingly used as an endpoint for assessment of efficacy in some trials so to assign			
this category when no lesions can be measured is not advised.			

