13.2 Sample Size/Accrual Rate

The primary goal of this Phase I trial is to determine the RP2D and assess safety of the combination regimen. A total of 6 -22 adolescent and young adult subjects will be accrued into the trial

It is anticipated that 0.5-1 subjects will be accrued per month so that study accrual will be completed within 36 months.

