13.4 Analysis of Primary and Secondary Endpoints

All patients who received study drug will be included in the safety analysis of this combination regimen. Dose-limiting toxicity rate, adverse event data and corresponding toxicity grades during the days of treatment will be summarized in each dose level and in the overall patient population. Incidence tables will be generated to summarize incidence of patients reporting at least one episode of each specific adverse event, incidence of adverse events causing withdrawal and incidence of serious adverse events. The total number of episodes for each event reported (Frequency Table), and the severity and attribution to study therapy of each episode reported (Severity Table and Attribution Table) will also be displayed.

Listings of adverse events by patients will include the time to onset, the duration of each event, the severity of each event, and the relationship of the event to study therapy, whether it was a serious event, and whether it caused withdrawal. Safety data will be summarized for the overall patient group and by dose levels. Toxicities will be graded according to Common Toxicity Criteria (CTCAE) v4.02.

Estimates of antitumor effect based on RECIST 1.1 criteria will be estimated. Furthermore,

Protocol # 15-0659 Version Date: March 22, 2017

specific PD parameters will be assessed including SN-38 and SN-38 glucuronide. Descriptive statistics will be employed to summarize quantitative levels of PD parameters at each time point of follow-up while changes in PD from baseline will be calculated and compared using paired statistical tests. Pharmacokinetic modeling (two-compartment or non-compartmental models) will be employed to estimate several PK parameters (area under the concentration versus time curve, AUC, half-life, clearance, Cmax, etc). These analyses will be considered exploratory in this Phase I trial.

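### The only defined response set drops treated patients who were not re-evaluated or who stopped within cycle 1 without objective progression, and no all-treated response rate is planned (minor)

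*Combined protocol and SAP*

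**What the plan says.** Antitumor activity is secondary objective 1.2.3. Three parts of the combined protocol and SAP bear on how it is summarised.

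- **Section 11.1.1** defines who counts. Besides having disease at baseline, patients must "have received at least one cycle of therapy, and have had their disease re-evaluated will be considered evaluable for response". A note makes one exception: "Patients who exhibit objective disease progression prior to the end of cycle 1 will also be considered evaluable".
- **Section 13.4** contains the whole response analysis: "Estimates of antitumor effect based on RECIST 1.1 criteria will be estimated". It names an all-treated population, but for another purpose: "All patients who received study drug will be included in the safety analysis of this combination regimen". The paragraph covering response and pharmacology ends: "These analyses will be considered exploratory in this Phase I trial".
- **Sections 10 and 11.1.4.3** set the assessments. The first scheduled on-treatment disease evaluation falls on days 15 to 21 of cycle 2, and another is listed at the end of treatment. Patients who stop for declining health without objective progression are recorded as having symptomatic deterioration, and sites are asked to try to document progression afterwards.

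On numbers, Section 13.2 says: "A total of 6 -22 adolescent and young adult subjects will be accrued into the trial". Section 5.6 says: "Once the RP2D is identified, an additional 10 patients will be enrolled at this dose level".

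**The concern.** Membership of the response set depends on what happens after treatment starts. A treated patient who dies, withdraws or misses the off-treatment evaluation before any re-assessment is outside it. So is a patient who stops within cycle 1 without objective progression. These events can be related to outcome, and the first scheduled re-assessment is late enough for them to occur: if cycle 1 lasts 21 days, it falls on days 36 to 42 (21 + 15 to 21 + 21).

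The plan does not ask for the number left out, or the reasons, to be reported. At stake is how the response proportion for objective 1.2.3 is read. Section 2.1 says the study is meant to inform the design of a Phase II trial of the combination's activity, so the denominator should be explicit.

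**Working it through.** **The plan's own figure.** The stated maximum of 22 is reproduced by two dose levels of 6 plus the expansion: 2 × 6 + 10 = 22. The lower figure is 3 + 3 = 6. The number at the recommended dose is 6 + 10 = 16. No response rate, response sample size or non-evaluable rate is stated, so there is no response figure to reproduce.

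**Inputs.** N = 16 or 22 comes from Sections 5.6 and 13.2. The number excluded (d = 1 to 4), responders among the evaluable (x = 3) and responders among the excluded (r = 0 or 1) are assumptions.

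**Formula.** The evaluable-only rate is x/(N − d) and the all-treated rate is (x + r)/N. Exclusion raises the reported rate only if r/d < x/(N − d). With r = 0 the inflation factor is N/(N − d).

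**Patients with no post-baseline assessment.** They have no recorded response, so r = 0 and the shift is upward whenever x is at least 1.

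| N | d = 1 | d = 2 | d = 3 | d = 4 |
|---|---|---|---|---|
| 16 | 1.067 | 1.143 | 1.231 | 1.333 |
| 22 | 1.048 | 1.100 | 1.158 | 1.222 |

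For x = 3 and d = 4, with exact (Clopper-Pearson) 95% intervals:

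- N = 16: 3/12 = 25.0% (5.5 to 57.2) against 3/16 = 18.8% (4.0 to 45.6). The shift is 25.00 − 18.75 = 6.25 points; the all-treated interval is 45.6 − 4.0 = 41.6 points wide.
- N = 22: 3/18 = 16.7% (3.6 to 41.4) against 3/22 = 13.6% (2.9 to 34.9). The shift is about 3.0 points; the all-treated interval is 34.9 − 2.9 = 32.0 points wide.

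**Patients who stop within cycle 1 without objective progression.** They fail the one-cycle condition even if scanned when treatment ends. Two facts limit their number: receiving at least one cycle is not defined, and all cycle 1 eribulin and irinotecan is scheduled by day 8. The direction of the shift is not fixed for them either. The four-week confirmation requirement carries the footnote "Only for non-randomized trials with response as primary endpoint", and response is not the primary endpoint here, so a single off-treatment evaluation could record a response. With d = 1 and r = 1 at N = 16, the comparison is 3/15 = 20.0% against 4/16 = 25.0%, and exclusion lowers the rate. This is possible but unlikely.

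**The case against.** The strongest reply is that little is lost. Response is secondary, the analysis is labelled exploratory, no hypothesis or decision rule uses the rate, and the shifts above are well inside the intervals. All of that stands and limits the point to minor.

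Three stronger readings are tempting, and the documents do not support them.

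- *That 13.4 adopts the evaluable set or rules out an all-treated rate.* It does neither. It names no response denominator; the evaluable set is inferred from 11.1.1, the only place where a response population is defined.
- *That a reader could not tell how far the rate had moved.* The safety analysis covers every treated patient, so if response is reported as x of n evaluable, the number excluded follows by subtraction and the rate can be bounded. For 3 of 12 evaluable among 16 treated, the all-treated rate lies between 3/16 = 18.8% and (3 + 4)/16 = 43.8%. What the plan fails to secure is an explicit count and the reasons.
- *That everyone who stops early disappears.* The off-treatment evaluation and the instruction to document progression after discontinuation bring some back: those who had received a cycle and are then re-evaluated, and those whose objective progression is shown before the end of cycle 1. The unassessed group is mainly early deaths, withdrawals and missed off-treatment evaluations.

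What remains is that the one defined response set selects on post-treatment events, and the plan sets no all-treated rate beside it.

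**Conclusion.** The point holds as a minor one. Read together, 11.1.1 and 13.4 imply a response proportion that leaves out some treated patients because of events after the start of treatment. For those never re-assessed, the effect is upward whenever there is a responder. For those who stop within cycle 1 without objective progression, it is usually upward but could reverse, and the group may be nearly empty.

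For 1 to 4 non-responding exclusions, the inflation is 1.07- to 1.33-fold at N = 16 and 1.05- to 1.22-fold at N = 22. These sizes rest on assumed exclusions and the absolute rates also on assumed responses. The gap in the text does not depend on either. The recommended dose rests on first-cycle dose-limiting toxicity and is not affected.

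**What to change.** Amend 11.1.1 and 13.4 along these lines:

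> The objective response rate is the proportion with a best overall response of CR or PR, recorded from the start of treatment until progression or off-study (including the start of a new regimen), among all patients with disease at baseline who received at least one dose of eribulin or irinotecan. It is given with an exact 95% confidence interval. Patients without a post-baseline assessment count as non-responders. Their number, with reasons, is reported. The evaluable-only rate is supportive.

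The time limits follow 11.1.4.3 and 5.10. Naming eribulin or irinotecan settles the position of a patient who took only cefixime, since Section 10 counts cefixime as the start of protocol therapy but not of chemotherapy.

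The cost is a wording amendment using data already collected, with no added visits, tests or patients. The reported rate may be slightly lower than the evaluable-only rate.

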11.1.2 Disease Parameters

Measurable disease. Measurable lesions are defined as those that can be accurately measured in at least one dimension (longest diameter to be recorded) as ≥ 20 mm by chest x-ray or as ≥ 10 mm with CT scan, MRI, or calipers by clinical exam. All tumor measurements must be recorded in millimeters (or decimal fractions of centimeters).

Note: Tumor lesions that are situated in a previously irradiated area may only be considered measurable if there is documentation of residual viable disease after irradiation, or if there is unequivocal progression at that site following irradiation.

Malignant lymph nodes. To be considered pathologically enlarged and measurable, a lymph node must be ≥ 15 mm in short axis when assessed by CT scan (CT scan slice thickness recommended to be no greater than 5 mm). At baseline and in follow-up, only the short axis will be measured and followed.

Evaluable Disease (also termed "non-measurable" or "non-target" disease). All other lesions (or sites of disease), including smaller pathologic lymph nodes are considered evaluable disease. Bone lesions, leptomeningeal disease, ascites, pleural/pericardial effusions, lymphangitis cutis/pulmonitis, inflammatory breast disease, and abdominal

masses (not followed by CT or MRI), are also considered as evaluable (non-measurable).

Note: Cystic lesions that meet the criteria for radiographically defined simple cysts should not be considered as malignant lesions (neither measurable nor evaluable (non-measurable)) since they are, by definition, simple cysts.

'Cystic lesions' thought to represent cystic metastases can be considered as measurable lesions, if they meet the definition of measurability described above. However, if non-cystic lesions are present in the same patient, these are preferred for selection as target lesions.

Target lesions. All measurable lesions up to a maximum of 2 lesions per organ and 5 lesions in total, representative of all involved organs, should be identified as **target lesions** and recorded and measured at baseline. Target lesions should be selected on the basis of their size (lesions with the longest diameter), be representative of all involved organs, but in addition should be those that lend themselves to reproducible repeated measurements. It may be the case that, on occasion, the largest lesion does not lend itself to reproducible measurement in which circumstance the next largest lesion which can be measured reproducibly should be selected. A sum of the diameters (longest for non-nodal lesions, short axis for nodal lesions) for all target lesions will be calculated and reported as the baseline sum diameters. If lymph nodes are to be included in the sum, then only the short axis is added into the sum. The baseline sum diameters will be used as reference to further characterize any objective tumor regression in the measurable dimension of the disease.

Non-target lesions. All other lesions (or sites of disease) including any evaluable (nonmeasurable) and measurable lesions over and above the 5 target lesions should be identified as **non-target lesions** and should also be recorded at baseline. Measurements of these lesions are not required, but the presence, absence, or in rare cases unequivocal progression of each should be noted throughout follow-up.

11.1.3 Methods for Evaluation of Measurable Disease

All measurements should be taken and recorded in metric notation using a ruler or calipers. All baseline evaluations should be performed as closely as possible to the beginning of treatment and never more than weeks before the beginning of the treatment.

The same method of assessment and the same technique should be used to characterize each identified and reported lesion at baseline and during follow-up. Imaging-based evaluation is preferred to evaluation by clinical examination unless the lesion(s) being followed cannot be imaged but are assessable by clinical exam.

Clinical lesions Clinical lesions will only be considered measurable when they are superficial (*e.g.*, skin nodules and palpable lymph nodes) and ≥ 10 mm diameter as assessed using calipers (*e.g.*, skin nodules). In the case of skin lesions, documentation by color photography, including a ruler to estimate the size of the lesion, is recommended.

Chest x-ray Lesions on chest x-ray are acceptable as measurable lesions when they are clearly defined and surrounded by aerated lung. However, CT is preferable.

Conventional CT and MRI This guideline has defined measurability of lesions on CT scan based on the assumption that CT slice thickness is 5 mm or less. If CT scans have slice thickness greater than 5 mm, the minimum size for a measurable lesion should be twice the slice thickness. MRI is also acceptable in certain situations (*e.g.* for body scans).

Use of MRI remains a complex issue. MRI has excellent contrast, spatial, and temporal resolution; however, there are many image acquisition variables involved in MRI, which greatly impact image quality, lesion conspicuity, and measurement. Furthermore, the availability of MRI is variable globally. As with CT, if an MRI is performed, the technical specifications of the scanning sequences used should be optimized for the evaluation of the type and site of disease. Furthermore, as with CT, the modality used at follow-up should be the same as was used at baseline and the lesions should be measured/assessed on the same pulse sequence. It is beyond the scope of the RECIST guidelines to prescribe specific MRI pulse sequence parameters for all scanners, body parts, and diseases. Ideally, the same type of scanner should be used and the image acquisition protocol should be followed as closely as possible to prior scans. Body scans should be performed with breath-hold scanning techniques, if possible.

PET-CT At present, the low dose or attenuation correction CT portion of a combined PET-CT is not always of optimal diagnostic CT quality for use with RECIST measurements. However, if it can be documented that the CT performed as part of a PET-CT is of identical diagnostic quality to a diagnostic CT (with IV and oral contrast), then the CT portion of the PET-CT can be used for RECIST measurements and can be used interchangeably with conventional CT in accurately measuring cancer lesions over time. Note, however, that the PET portion of the CT introduces additional data which may bias an investigator if it is not routinely or serially performed. Ultrasound Ultrasound is not useful in assessment of lesion size and should not be used as a method of measurement. Ultrasound examinations cannot be reproduced in their entirety for independent review at a later date and, because they are operator dependent, it cannot be guaranteed that the same technique and measurements will be taken from one assessment to the next. If new lesions are identified by ultrasound in the cycle of the study, confirmation by CT or MRI is advised. If there is concern about radiation exposure at CT, MRI may be used instead of CT in selected instances.

Endoscopy, Laparoscopy The utilization of these techniques for objective tumor evaluation is not advised. However, such techniques may be useful to confirm complete pathological response when biopsies are obtained or to determine relapse in trials where recurrence following complete response (CR) or surgical resection is an endpoint.

Tumor markers Tumor markers alone cannot be used to assess response. If markers are initially above the upper normal limit, they must normalize for a patient to be considered

in complete clinical response. Specific guidelines for both CA-125 response (in recurrent ovarian cancer) and PSA response (in recurrent prostate cancer) have been published [66-68]. In addition, the Gynecologic Cancer Intergroup has developed CA-125 progression criteria which are to be integrated with objective tumor assessment for use in first-line trials in ovarian cancer [69].

Cytology, Histology These techniques can be used to differentiate between partial responses (PR) and complete responses (CR) in rare cases (*e.g.*, residual lesions in tumor types, such as germ cell tumors, where known residual benign tumors can remain).

The cytological confirmation of the neoplastic origin of any effusion that appears or worsens during treatment when the measurable tumor has met criteria for response or stable disease is mandatory to differentiate between response or stable disease (an effusion may be a side effect of the treatment) and progressive disease.

FDG-PET While FDG-PET response assessments need additional study, it is sometimes reasonable to incorporate the use of FDG-PET scanning to complement CT scanning in assessment of progression (particularly possible 'new' disease). New lesions on the basis of FDG-PET imaging can be identified according to the following algorithm:

- a. Negative FDG-PET at baseline, with a positive FDG-PET at follow-up is a sign of PD based on a new lesion.
- b. No FDG-PET at baseline and a positive FDG-PET at follow-up: If the positive FDG-PET at follow-up corresponds to a new site of disease confirmed by CT, this is PD. If the positive FDG-PET at follow-up is not confirmed as a new site of disease on CT, additional follow-up CT scans are needed to determine if there is truly progression occurring at that site (if so, the date of PD will be the date of the initial abnormal FDG-PET scan). If the positive FDG-PET at follow-up corresponds to a pre-existing site of disease on CT that is not progressing on the basis of the anatomic images, this is not PD.
- c. FDG-PET may be used to upgrade a response to a CR in a manner similar to a biopsy in cases where a residual radiographic abnormality is thought to represent fibrosis or scarring.

Note: A 'positive' FDG-PET scan lesion means one which is FDG avid with an uptake greater than twice that of the surrounding tissue on the attenuation corrected image.

11.1.4 Response Criteria

